A student participant in Stage 1 showing significant worsening may be re-randomized to Stage 2 conditions earlier. Similarly, students who begin the study with significant suicidality and show no improvement after 4 sessions may also be considered for early randomization to Stage 2.

Primary DV: Suicide-Related Behaviors – Relevant to Aims 1, 2, and 3.

Recognizing that measurement of suicide-related behaviors is fraught with challenges,¹¹² we are defining SR as “suicidal ideation, attitudes, behaviors and plans which take into account severity, intent, and ability to cope with ideation without engaging in suicidal behaviors, such as planning/rehearsal, NSSI, suicide attempts (SAs), and suicide.” Our primary assessment measures for SR are two interviews to measure suicidal ideation (SI; defined as self-reported thoughts of suicide-related behavior) and suicidal behaviors, including suicide attempts and non-suicidal self-injury (NSSI). Suicides will also be tallied.

- 1) The Scale for Suicide Ideation—Current (SSI)^{99,113} is a 19-question interview that assesses the student participant’s highest SI in the past 2 weeks, including attitudes, behaviors, and plans. Each item is rated as 0,1, or 2 with a total scale of 0-38. The IEs will be trained and certified on the SSI.
- 2) The Self-Injurious Thoughts and Behaviors Interview (SITBI)¹¹⁴ is a 3-15-minute interview containing modules that assess SI, suicide plans, suicide gestures, suicide attempts, and NSSI. The SITBI has been used with college students.^{115,116} The IEs will be trained and certified on the SITBI.

Secondary DVs/Covariates: Functioning – Relevant to All Aims

- 1) The CCAPS-34¹⁰⁷ assesses key domains of college student mental health (Depression, Generalized Anxiety, Social Anxiety, Academic Distress, Eating Concerns, Substance Use, and Hostility/Anger) and an overall Distress Index score. Students respond to questions using a 5-point rating scale (“*not at all like me*” to “*extremely like me*”). The CCAPS-34 takes only 2-3 minutes to complete¹⁰⁷ and is widely used in CCCs.²²¹ The CCAPS will be assessed at all assessment points and at every session. The question on SI will screen prospective participants and the weekly administration can track SI fluctuations more frequently.

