- 1) Client Satisfaction Questionnaire (CSQ-8)¹³⁶ is an 8-item questionnaire that assesses clients' satisfaction with treatment and has been used in other CAMS studies.⁶⁶ See Preliminary Studies.
- 2) CSQ-8 (Therapist Version) and Reasons for Termination Checklist. Counselor participants' acceptability of and satisfaction with the interventions will be assessed at the end of Stage 1 and Stage 2 via the therapist version of the CSQ and Reasons for Termination Checklist. These measures were used in other CAMS⁶⁶ studies and our pilot.
- 3) Treatment Credibility Questionnaire. After session 1 of each stage, student participants will rate the therapy they are receiving on seven items adapted from Borkovec and Nau¹³⁷ that ask how logical, scientific, or potentially helpful the treatment appears to be.
- 4) Therapist Expectations. Two Likert-style questions regarding expectations about treatment utilized in prior studies⁶⁶ will be completed by counselor participants at the end of the first session in Stage 1 and Stage 2.
- 5) Treatment History Interview (THI)¹³⁸ is an interview to gather information about a client's psychiatric and medical treatment over a period of time, including psychotherapy, comprehensive treatment programs, case management, self-help groups, inpatient units, emergency treatment (e.g., emergency room visits, police wellness checks), medical treatment, as well as the use of psychotropic and other medications. The THI will be

collected at baseline, end of Stage 2, and follow-up. Data will be utilized descriptively and for cost analyses.

- 6) Telehealth Usability Questionnaire (TUQ)¹⁸⁷ is a 15-item questionnaire that assesses student participants' acceptability with using telehealth platforms for therapy.
- 7) TUQ-C (Counselor Version) is an adapted version of the TUQ questionnaire that assesses counselor participants' acceptability with using telehealth platforms for therapy. Counselors who provide DBT skills training via telehealth will also complete an adapted TUQ for DBT skills training.
- 8) Focused Interview. Counselor participants will each complete a focused interview at the end of their participation in the study. An independent party will conduct the focused interviews, which will center on each participant's experience of the study.

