9.3 CAMPUS TRIAL STATISTICAL ANALYSES

9.3.1 GENERAL APPROACH

Overview and Intent-to-Treat. The proposed trial design of adaptive treatment strategies (ATSSs) is like a factorial design;^{156,157,158,159} different analytic subgroups (see Table 8) are combined to answer different questions. Aim 1 is the trial's primary aim; Aims 2-5 are secondary aims and Aim 6 as an implementation aim. All student participants, once randomized, will be included in the intent-to-treat sample, and every effort will be made to collect all primary and secondary outcomes even if a student participant does not engage in randomly assigned treatments. The primary outcome of interest is suicidal risk, which includes suicidal ideation as well as suicide-related behaviors, such as non-suicidal self-injury (NSSI) and suicide attempts (SAs); however suicidal ideation is the primary DV due to relatively low rates of suicidal behaviors post-baseline with college students. Suicides will be tallied as well. All analyses allow for the inclusion of covariates listed as demographics and covariates in Section 8.1. Covariates will enter the model based in clinical importance (gender, age, current alcohol use, current substance use, etc.) and retained on a case-by-case basis based on statistical significance.

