9.3.7 EXPLORATORY ANALYSES

Aim 6 analyses focus on the implementation of ATSSs within CCC settings. Descriptive statistics with confidence intervals will be derived for the implementation outcomes within Stage 1 and Stage 2 separately. For student participant level measures nested within counselor, we will implement HLM to account for the clustering attributable to student participants within counselor. A benchmarking procedure will be used to compare various treatment combinations.¹⁷⁶ Stakeholder interviews and the quarterly CCIAB meetings will be audio-recorded for subsequent transcription. Thematic content analysis techniques will be used to analyze the transcript text. Data management and data reduction will be accomplished using the ATLAS-ti text-analysis software. To examine the efficiency of alternative intervention strategies, we will estimate the service costs for each of the four ATSSs. Our cost analyses consider both the payer perspective, focusing on service costs, as well as the patient perspective, focusing on cost-effectiveness, which considers health outcomes in addition to service costs. Psychological service utilization will be measured primarily through EMRs from the CCCs and through health care visits at the student health centers. To capture services outside of the universities, the Treatment History Interview (THI) will be administered at follow-up. Service utilization will be converted to monetary costs using average reimbursement rates for the corresponding category of services in the national Medical Expenditure Panel Survey (MEPS). We will also query each site about any local reimbursement rates, to examine comparability with the MEPS data and to gain a sense of potential variability across regions. In addition to service costs, implementation costs such as participation in trainings and

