supervision corresponding to the intervention will be tracked using logs of personnel time (and multiplied by corresponding wage and facility overhead rates). To make cost-effectiveness comparisons, incremental cost-effective ratios (ICERs) will be calculated as the incremental cost divided by the incremental clinical benefits (e.g., remission rate of suicide risk) for each pairwise comparison of intervention strategies. Uncertainty surrounding these estimates will be calculated as cost-effectiveness acceptability curves and confidence intervals, using bootstrapping with Monte Carlo simulations. In addition, we will conduct an exploratory analysis of the “hidden costs” to college campuses associated with not providing adequate treatment for students experiencing suicidal ideation and behaviors (e.g., crises on campus, NSSI in residence halls).

Aim 7 analyses focus on the experience of counselors in the study. Given the relatively small sample size, the fact that the same counselors will be administering all treatments, and no *a priori* hypotheses, we regard these analyses as exploratory. Counselors will be divided into clinically relevant groups based on cut-points on key demographic variables (e.g., age, gender, years of overall experience, years of *experience* treating suicidal students, etc.). Analyses of variance will be used to examine differences in continuous outcomes; logistic regression analyses and contingency table analyses will be used to analyze differences in dichotomous outcomes. we will also use effect size benchmarks and descriptive statistics to gauge potentially meaningful effects (e.g., eta-square > .06; odd ratios > 2.0).

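### The exploratory strategy cost comparison gives the baseline service-use interview no role, so an inexpensive precision gain is left unspecified

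*Combined protocol and SAP*

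**What the plan says.** Section 9.3.7 costs the four strategies from counseling-center records, student health visits and the THI, and adds training and supervision time. For care outside the university it states: "To capture services outside of the universities, the Treatment History Interview (THI) will be administered at follow-up". The comparison is then defined: "incremental cost-effective ratios (ICERs) will be calculated as the incremental cost divided by the incremental clinical benefits". For uncertainty: "Uncertainty surrounding these estimates will be calculated as cost-effectiveness acceptability curves and confidence intervals, using bootstrapping with Monte Carlo simulations". No regression model, covariate or baseline cost is named.

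Section 8.1 describes the THI as covering psychotherapy, inpatient and emergency care, medical treatment and medication, and says it is "collected at baseline, end of Stage 2, and follow-up. Data will be utilized descriptively and for cost analyses". Table 1 also schedules it before treatment starts.

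Section 9.3.1 has a general rule: "All analyses allow for the inclusion of covariates listed as demographics and covariates in Section 8.1". Such covariates are "retained on a case-by-case basis based on statistical significance". The 8.1 heading that uses the word is "Secondary DVs/Covariates: Functioning – Relevant to All Aims". It holds the CCAPS-34, the CGI scales and academic functioning. The THI is listed separately, among the implementation and process measures.

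**The concern.** Section 1.1 names finding the most cost-effective sequence as a trial aim. Service costs are usually skewed and tend to repeat within a person, so a few students with heavy prior use who fall into one strategy can move its mean cost. Prior service use is not a balancing factor in the randomisation (6.3). The clinical mixed models for Aims 2 and 8 prespecify adjustment for site, age, race and clinical severity; the cost comparison has no equivalent, although a measure of prior service use is collected. At stake are the width of the interval for the cost difference, and whether the decision to adjust is made before or after the data are seen.

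**Working it through.** The plan states no SD, sample size or power for the cost analysis, so there is no figure of its own to reproduce on this point. As a check on the arm sizes only, Aim 2 (240 per arm, d = 0.30, two-sided 2.5%) gives 85.2% power against the stated 85%.

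**Inputs from the documents.** N = 480, 240 per Stage 1 arm, 50% response (4.2, 9.2). There are 60 non-responders per Stage 2 path, or 45 after 25% attrition (9.2). Weights come from the randomisation probabilities (9.3.2): 2 for responders and 4 for non-responders under equal allocation. I assume that strategy mean costs are weighted in the same way.

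**Assumed, not in the documents.** The correlation ρ between baseline and study cost.

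**Effective sample size per strategy**, (Σw)²/Σw²:
- 60 per path: Σw = 120×2 + 60×4 = 480; Σw² = 120×4 + 60×16 = 1,440; 480²/1,440 = 160.
- 45 per path: Σw = 420; Σw² = 1,200; 420²/1,200 = 147.

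**Chance imbalance in mean baseline cost**, strategies with different Stage 1 treatments: √(2/160) = 0.112 SD and √(2/147) = 0.117 SD. The 95% range (×1.96) is ±0.22 to ±0.23 SD. For strategies sharing a Stage 1 treatment only the non-responders differ, and the range is about ±0.18 SD.

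**What reaches the cost difference** is ρ times that imbalance. Adjustment removes a share ρ² of the variance, equivalent to 480/(1 − ρ²) students:

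| ρ | 95% imbalance carried over (cost SD) | Variance cut | SE cut | Equivalent N |
|---|---|---|---|---|
| 0.1 | ±0.02 | 1% | 0.5% | 485 |
| 0.2 | ±0.04 to 0.05 | 4% | 2% | 500 |
| 0.3 | ±0.07 | 9% | 5% | 527 |
| 0.5 | ±0.11 | 25% | 13% | 640 |
| 0.6 | ±0.13 to 0.14 | 36% | 20% | 750 |

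**Simulation check.** 4,000 simulated trials were run at each of ρ = 0.3, 0.5 and 0.7, with lognormal costs, no true difference, response unrelated to cost, and no missing data. Adjusted-to-unadjusted SE ratios were 0.94, 0.85 and 0.69, against 0.95, 0.87 and 0.71 from √(1 − ρ²). The mean unadjusted difference was within 0.003 SD of zero. Its 95% interval, using a sandwich SE and not the planned bootstrap, covered 94.8% to 95.2%.

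**The case against.** Four stronger readings are tempting, and the documents support none of them.

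- *A reader might infer that the plan mandates raw costs and ignores the baseline interview.* It does neither. An incremental cost over an incremental benefit is the definition of the ratio and fits adjusted increments equally well, and 8.1 assigns THI data to cost analyses with the baseline wave included. The plan is silent on how that wave is used.
- *A reader might infer bias.* Chance imbalance is sampling error. Randomisation keeps the unadjusted contrast unbiased, and a valid interval already reflects that error.
- *A reader might take the imbalance in prior cost as the error in the result.* With an assumed cost SD of 2 to 3 times the mean, 0.112 SD is 22% to 34% of mean prior cost. That describes prior cost; only the fraction ρ, in SD units, carries into the incremental cost.
- *A reader might apply the equivalent sample sizes to the cost-effectiveness ratio.* Its uncertainty also depends on the effect difference, which this adjustment leaves alone.

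The design also limits the problem. Students seen at the counseling center in the last three months are excluded (5.2), and randomisation balances on previous attempts and current psychotropic medication (6.3), both plausible markers of prior use. Study costs come primarily from campus records, and training and supervision costs have no baseline counterpart. All of this makes a low ρ credible.

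The covariate list in 9.3.1 is open-ended, and its alcohol and substance-use examples have dedicated measures under the moderator heading of 8.1, so a strict heading-based reading is contestable. Even on the generous reading, retention by statistical significance leaves adjustment of a skewed outcome to be settled after the data are seen. That part of the point stands.

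**Conclusion.** The point holds as an inexpensive improvement to an exploratory analysis. The primary result is unaffected. No baseline-cost adjustment is specified, 9.3.7 and 8.1 differ on when the THI is given, and 9.3.1 does not supply the adjustment. The loss is precision in the cost difference and protection against imbalance in the realised sample. Its size rests on an undocumented correlation: a 9% to 36% variance reduction at 0.3 to 0.6, and 1% to 4% at 0.1 to 0.2.

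**What to change.** - In 9.3.7, state the THI time points as in 8.1: baseline, end of Stage 2 and follow-up.
- Prespecify baseline THI service cost as a covariate in the strategy-weighted cost model. Keep it whatever its significance, and refit the model within each bootstrap replicate.
- Report the unadjusted result as a sensitivity analysis.
- Confirm and state the THI's baseline recall window. Section 5.4 gives the last six months only as a generic baseline timeframe, and the THI entry in 8.1 gives no specific period.

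The cost is SAP wording, a few lines of code, and pricing the baseline interview with the same price list. No new data are needed.

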location/preference of the counselor participant. In addition, we are proposing modifications to the overall length of the trial and the treatments to better fit within the CCC setting.

The multisite CAMPUS Trial will enroll moderately to severely suicidal college students in the “emerging adulthood” phase (ages 18-25) seeking services at CCCs and evaluate the relative effectiveness of the adaptive treatment strategies (ATSSs) when delivered via a hybrid model. The four ATSSs will be developed and refined within the context of the current sequential multiple assignment randomized trial (SMART). The SMART will have two stages of intervention. In Stage 1, 480 participants from the participating CCCs will be randomized to 4-6 weeks of: (1) a suicide-focused treatment – Collaborative Assessment and Management of Suicidality (CAMS) or (2) Treatment as Usual (TAU).

Sufficient responders to either intervention will enter the maintenance phase. Non-responders will be re-randomized to one of two Stage 2 higher intensity/dosage intervention options for an additional 1-8 weeks: (1) CAMS (either continued or administered for the first time) or (2) Counseling Center Dialectical Behavior Therapy Dialectical Behavioral Therapy for College Counseling settings (CC-DBT), which includes individual therapy and skills training.

For the CAMPUS Trial, we will also enroll up to 40 CCC counselors who will serve as study counselor participants and periodically complete measures focused on the experience of counselors working with suicidal college students.

Objectives: The overall purpose of the multisite CAMPUS Trial is to evaluate the relative effectiveness of four adaptive treatment strategies (ATSSs) to treat college students who report suicidal ideation when first seeking services at their college counseling center.

The CAMPUS Trial aims to identify which sequence(s) of treatments are most effective on average (average treatment effect or ATE), which treatment sequence(s) are most cost-effective for college counseling centers to provide, and whether outcomes vary based on key student characteristics (heterogeneity of treatment effect or HTE).

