5.1 INCLUSION CRITERIA

College Students. We will recruit N=480 male, female, and transgender/nonbinary college students across the participating sites for the CAMPUS trial. Inclusion criteria to participate in the study consists of:

- (1) Enrolled at the university.
- (2) Eligible to receive counseling services either in person or remotely at the campus CCC.
- (3) 18 to 25 years of age.
- (4) Moderate to severe SI over the last two weeks indicated by one or more of the following:
 - A score of ≥ 2 on the Counseling Center Assessment of Psychological Symptoms (CCAPS) question, "I have thoughts of ending my life."
 - Self-report during clinical interview at intake
 - Other intake questionnaires given as standard clinical practice at CCCs (e.g., C-SSRS)
- (5) Suicidality is a focus of treatment
- (6) Agree to video recording of all therapy and assessment sessions.

CCC Counselors

We will recruit approximately N≈24 counselor participants across all participating sites. The number of counselor participants may increase or decrease throughout the project based on turnover, but we expect to maintain approximately 24 participating counselors at a time in each of the enrollment years.

Inclusion criteria to participate in the study consists of:

1. Currently or soon to be employed as a counselor or trainee at the CCC for at least the next year;
2. Willingness to work with suicidal college students;
3. Interested in learning to implement Collaborative Assessment and Management of Suicidality (CAMS) and Dialectical Behavioral Therapy for College Counseling settings (CC-DBT);
4. Willing to attend trainings in CAMS and CC-DBT;
5. Willing to have therapy sessions video-recorded and rated for adherence to the treatment model;
6. Interested in attending weekly consultation meetings to improve the quality and adherence of study treatments; and
7. Willing to complete measures about themselves and their student participants.

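### Aim 7's raw eta-square benchmark of .06 is exceeded by chance in 13-74% of counselor comparisons at 24-40 counselors; a bias-corrected index with confidence intervals would serve better

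*Combined protocol and SAP*

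**What the plan says.** Section 9.3.7 sets out the Aim 7 analysis: "Counselors will be divided into clinically relevant groups based on cut-points on key demographic variables", with age, gender and two kinds of experience named as examples. The methods are conventional: "Analyses of variance will be used to examine differences in continuous outcomes", and "logistic regression analyses and contingency table analyses will be used to analyze differences in dichotomous outcomes". The plan then adds "effect size benchmarks and descriptive statistics to gauge potentially meaningful effects (e.g., eta-square > .06; odd ratios > 2.0".

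On sample size, the Synopsis says "we will also enroll up to 40 CCC counselors", while section 5.1 says "we expect to maintain approximately 24 participating counselors at a time".

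Section 9.3.7 gives the small number of counselors, the fact that the same counselors deliver all treatments, and the lack of prior hypotheses as reasons for treating Aim 7 as exploratory. The Synopsis and Table 2 also call it exploratory. The plan does not give the number of groups, the cut-points or the number of comparisons. It attaches no confidence interval to the Aim 7 effect sizes, although the Aim 6 paragraph of the same section promises intervals for its descriptive statistics.

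**The concern.** An eta-square of .06 or an odds ratio of 2 is a reasonable marker of a moderate effect in the population. The plan, however, compares the sample value with it. Sample eta-square cannot be negative and absorbs noise in proportion to the number of groups, so with a few dozen counselors it often passes .06 when nothing is there. The sample odds ratio is not bounded in the same way, but at this size it is imprecise enough to stray past 2 often.

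What is at stake is how counselor findings are described. A reader told that a characteristic showed a potentially meaningful effect would not know how readily chance produces that label.

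**Working it through.** The documents give no power, precision or error rate for Aim 7, so there is no plan figure to reproduce.

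**Inputs.** Benchmarks: eta-square > .06 and odds ratio > 2.0 (section 9.3.7). Counselors: n = 24 (section 5.1) and n = 40 (Synopsis). Assumptions, because the plan is silent: k = 2 to 4 groups, one independent value per counselor, normal errors, and outcome prevalence of 30-50% for the main odds-ratio check.

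**Eta-square with no true difference.** It follows Beta((k-1)/2, (n-k)/2), with mean (k-1)/(n-1). Exceeding .06 is the same as F > [.06/(k-1)] / [.94/(n-k)] on k-1 and n-k degrees of freedom. For n=24 and k=2 the cut is .06/(.94/22) = 1.404, and P(F > 1.404) = 24.9%. For n=24 and k=3 it is .03/(.94/21) = 0.670, and P = 52.2%.

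**Bias-corrected indices at the same cut.**
- Omega-square = (k-1)(F-1) / [(k-1)(F-1) + n]. It exceeds .06 when F > 1 + .06n/[.94(k-1)]. For n=24 and k=2 that is 1 + 1.44/.94 = 2.532, and P = 12.6%.
- Epsilon-square = 1 - (1 - eta-square)(n-1)/(n-k). It exceeds .06 when eta-square > 1 - .94(n-k)/(n-1). For n=24 and k=2 that is .101, and P = 13.0%.

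| n | k | mean eta-square, no effect | P(eta-square > .06) | eta-square needed for p<.05 | P(omega-square > .06) | P(epsilon-square > .06) |
|---|---|---|---|---|---|---|
| 24 | 2 | .043 | 25% | .164 | 13% | 13% |
| 24 | 3 | .087 | 52% | .248 | 20% | 20% |
| 24 | 4 | .130 | 74% | .317 | 24% | 25% |
| 40 | 2 | .026 | 13% | .097 | 7% | 7% |
| 40 | 3 | .051 | 32% | .150 | 12% | 12% |
| 40 | 4 | .077 | 52% | .193 | 16% | 16% |

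With three groups at n=24, or four groups at either size, the average result under no effect is already above .06. In every row .06 lies below the value needed for p<.05.

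**Odds ratio with no true difference.** I enumerated two independent binomials with equal probability exactly, in equal groups, without a cell correction.

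| n | prevalence | P(OR > 2) | P(OR > 2 or < 0.5) |
|---|---|---|---|
| 24 (12 vs 12) | 50% | 17.9% | 35.8% |
| 24 (12 vs 12) | 30% | 24.1% | 48.2% |
| 40 (20 vs 20) | 50% | 13.5% | 27.0% |
| 40 (20 vs 20) | 30% | 15.8% | 31.7% |

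Adding 0.5 to each cell lowers the n=24 one-direction rates to 15.8-19.1% and leaves those at n=40 unchanged. Prevalence of 10-20% or unequal groups raises the either-direction rate to as much as about 73% (about 57% with the correction).

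**The case against.** The strongest reply is that the plan does not use these benchmarks as a decision rule. They come after the formal tests, are introduced as an addition, are given as examples and are paired with descriptive statistics. The aim is labelled exploratory throughout. All of this stands, and it limits the consequence to description.

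Three stronger readings are tempting, and the documents do not support them:
- *That the plan adopts the benchmarks because the sample is small.* Section 9.3.7 gives the small sample as a reason for calling the analyses exploratory, not as the reason for the benchmarks.
- *That a list of spurious counselor characteristics is all but guaranteed.* This would need the benchmark as the sole screen and a known number of independent comparisons. The plan states neither, and the grouping variables it names (age, overall experience, experience with suicidal students) are probably correlated.
- *That such findings will shape training or dissemination.* No section says that Aim 7 results will be used in this way.

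Two technical limits also stand. First, n=24 is the number expected at one time, so it is the low end. Second, some counselor forms, such as the TAU Questionnaire, are completed per student. The calculation does not describe those rows directly, although clustering by counselor would limit any gain in effective sample size.

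It would also be wrong to require the interval to exclude no effect before calling an effect potentially meaningful. That turns the gauge back into a significance test. For a true eta-square of .06 with two groups, power at the 5% level is only 22% (n=24) or 34% (n=40).

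The calibration problem remains. The exploratory label does not tell a reader how often chance alone passes the benchmark.

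**Conclusion.** The point holds as a minor, inexpensive improvement to an exploratory analysis. At the trial's own counselor numbers, raw eta-square passes .06 by chance in 13-74% of comparisons, depending on n (24-40) and the number of groups (2-4). An odds ratio above 2 does so in roughly 14-24% of balanced two-group comparisons with a 30-50% outcome. These figures rest on one value per counselor, normal errors for eta-square, and assumed group numbers and prevalence. The range is wide because the plan leaves these open. Primary and secondary inference is unaffected.

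**What to change.** Amend the Aim 7 paragraph of section 9.3.7 to:
- replace raw eta-square with omega-square or epsilon-square. At the .06 cut this brings the chance rate to about 13-25% (n=24) or 7-16% (n=40);
- report every effect size and odds ratio with its 95% confidence interval, in line with Aim 6. For the odds ratio the interval is the main safeguard, because the change of index does not touch it;
- state how many comparisons were examined;
- describe effects whose interval includes no effect as descriptive or hypothesis-generating, without requiring the interval to exclude no effect before an effect is reported.

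This costs a sentence or two and needs no new data. The downside is that somewhat fewer effects are highlighted, including some real ones. For a true eta-square of .06 with two groups, the noncentrality is n x .06/.94, or 1.53 at n=24 and 2.55 at n=40. The chance of passing the cut then falls from 53% with eta-square to 38% with omega-square at n=24, and from 52% to 39% at n=40.
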